## 8. Benefits

There is no direct benefit to individuals who chose to participate in this study. The potential benefits to study participants include improved care quality in the intervention arm if the individuation intervention proves beneficial. In addition, providers will have the opportunity to participate in educational sessions to help reduce unconscious bias, which may improve the care they provide to their patients. Additionally, society may benefit in the future from both increased care quality, reduced influence of bias on clinical decision-making, and the accumulated knowledge that originates from this research. Based on the information learned from this pilot study, the researchers aim to develop curriculum and design a larger multisite intervention to more broadly understand the impact of these biases on care and to help providers use tools to address them.

## 9. Statistical Analysis

Power calculations are based on Aim 1's primary outcome (quality metric score). We account for an intracluster correlation coefficient (ICC) of 0.02 among patients of the same provider and assume a two-sided alpha level of 0.05. With 10 providers in each arm (N=20) and 8 patients per provider (N=160), we would have 84% power to detect a mean difference between arms of 0.5SD. If the ICC is 0.05, we would have 84% power to detect the same mean difference if 10 patients per provider were included.

All analyses will follow intention-to-treat (ITT) principles. All analyses will follow intention-to-treat (ITT) principles. For Aim 1, unadjusted and adjusted linear generalized estimating equation (GEE) models that account for patient clustering by providers will be used, with the quality metric score as the primary dependent variable, intervention arm as the primary predictor variable and covariates including hospital, and other factors that are either strongly correlated with the dependent variable (e.g. rheumatic disease) or imbalanced between the arms. We will use Millisecond software to program the IATs and calculate D scores that reflect response times and compare these findings across the two groups. For Aim 2, unadjusted and adjusted linear GEE models will be constructed with a) communication metrics and b) models for each survey score as the dependent variables, intervention arm as the primary predictor variable, and covariates as above. We will also analyze the transcripts qualitatively using Dedoose software and use the constant comparison method to evaluate and refine our themes and our codes.

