### **3. General Description of Study Design**

We will conduct a cluster-randomized controlled trial. The clusters are 20 rheumatologists at multisite BWH and MGH-affiliated clinics. Rheumatologists will be stratified by hospital and by gender and randomly assigned. Ten rheumatologists will be assigned to the intervention arm and ten to the control. Assessments will be conducted for 8-10 patients per rheumatologist (max 100 patients total in each arm, 200 total). Randomization will be stratified by BWH and MGH Rheumatology main campus hospitals (MGH or BWH/ Faulkner (FH)) and their rheumatology satellite clinic sites, and by provider gender (male or female). Study schema is included as an attachment.

In addition to the 200 SLE, osteoarthritis, and inflammatory arthritis patients including RA who will be studied directly, we also will examine the medical records of patients with inflammatory arthritis, osteoarthritis, or SLE in the practices of the enrolled providers seen during the same study period. In addition to the chart review of patients who meet the inclusion criteria of less than 2 visits in the past year, we will perform a secondary analysis of all patients who may have been seen greater than 2 times in the past year as we anticipate a spillover effect from the intervention and would like to study

this. Patients who were approached to participate in the audiorecorded component of the trial and declined will not be included in this medical record review. We will have no direct interaction with these patients. Most medical records we will review will be for patients of enrolled providers who we had no direct interaction with. The goal of this chart review component is to more broadly examine the impact of the intervention on the quality measures described in Table 1 below, beyond those individuals who will have their encounters audiorecorded. In addition to allowing for a larger sample size for analysis, it also will allow for analyses that may not be influenced by the act of recording an encounter (e.g., possibly, due to the recording, care may be somewhat different from other patients in each providers' practice and this will allow us to capture both). For quality metrics that would only be a onetime screen or once every few years, we will review prior records to see if they were eligible for those outcomes (such as receipt of vaccinations).

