#### 5. Outcomes.

The primary outcome is documented receipt of high-quality care at the time of the appointment or within 30 days of the appointment (see Table 1). The items below will be added together to form a score and the number of items completed out of the total will be the primary outcome measure compared across groups. We will measure these data for all patients with SLE, osteoarthritis, and inflammatory arthritis including RA seen by the provider during the 6-month study period as well as do a separate subgroup analysis focused on the patients who had their appointments audiorecorded. We will use electronic medical record data obtained from chart review, from RPDR and from the Enterprise Data Warehouse (EDW) to obtain these metrics.

Table 1. Quality metrics for diseases of interest		
Systemic lupus erythematosus (SLE)	Rheumatoid Arthritis (RA)	Osteoarthritis
Hydroxychloroquine (HCQ) initiation If lupus nephritis, immunosuppressive initiation, ACE-I or ARB, glucocorticoids Glucocorticoid prophylaxis (e.g. PPI, calcium/vitamin D, PJP if high dose) Contraception if on teratogenic medication Vaccinations Baseline HCQ eye exam and monitoring labs	DMARD initiation, or bDMARD initiation Folic acid if receiving methotrexate Glucocorticoid prophylaxis Contraception if on teratogenic medication Baseline X-rays, TB and hepatitis screening Labs within 1 month of methotrexate initiation Documentation of disease activity measure Vaccinations	Annual functional status assessment Baseline exams Annual pain assessment Recommendation for assistive devices

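### Both 84% power figures use a large-sample formula; with 20 randomised providers a test that holds 5% has about 80% and 79% power, and no small-sample method is named for the GEE

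*Combined protocol and SAP*

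**What the plan says.** Section 3 fixes the randomised units: "The clusters are 20 rheumatologists at multisite BWH and MGH-affiliated clinics", ten per arm. Section 9 bases power on the Aim 1 quality metric score and says the authors "assume a two-sided alpha level of 0.05". The base case is "We account for an intracluster correlation coefficient (ICC) of 0.02 among patients of the same provider", and its result is "With 10 providers in each arm (N=20) and 8 patients per provider (N=160), we would have 84% power to detect a mean difference" of half a standard deviation. The second case is "If the ICC is 0.05, we would have 84% power to detect the same mean difference if 10 patients per provider were included".

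For the Aim 1 analysis, Section 9 says that "unadjusted and adjusted linear generalized estimating equation (GEE) models that account for patient clustering by providers will be used". Hospital is a named covariate, and Aim 2 uses the same type of model. Neither Section 9 nor any other section names a variance estimator, a reference distribution, degrees of freedom, a small-sample correction or a permutation test. The power statement does not say which distribution it used.

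The chart review described in Section 3 may enlarge the clusters beyond 8 to 10 patients ("In addition to allowing for a larger sample size for analysis"). The Outcomes part of Section 6 says of the primary outcome: "We will measure these data for all patients with SLE, osteoarthritis, and inflammatory arthritis including RA seen by the provider" in the 6-month study period.

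**The concern.** The arm effect is a contrast between 10 providers and 10 providers, so the information about its standard error comes from 20 units, however many patients each contributes. A normal critical value treats that standard error as known. With 18 degrees of freedom it is not, and power read from the normal curve is too high for a test that really holds 5%.

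The same shortage of clusters affects the analysis. The standard GEE sandwich variance is biased downwards with few clusters, and a z reference adds to the problem. Section 9 neither excludes a correction nor requires one, so the choice could be made after the data are seen. Aim 1 is framed as a test of efficacy, and Section 8 says that the findings will feed a larger multisite intervention. A nominal 5% that is really 8 or 9% would matter there.

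**Working it through.** **Inputs (Sections 3 and 9).** k = 10 providers per arm; difference 0.5 SD; two-sided alpha 0.05; case A: m = 8 patients per provider, ICC 0.02; case B: m = 10, ICC 0.05. No loss is built into the plan's calculation, so none is applied here.

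**Step 1: reproduce the plan's figures.** Design effect DE = 1 + (m − 1) × ICC; effective n per arm = 10m/DE; noncentrality = 0.5 × √(effective n / 2); power ≈ Φ(noncentrality − 1.96).

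- Case A: DE = 1 + 7 × 0.02 = 1.14; effective n = 80/1.14 = 70.18; noncentrality 2.962; power 84.2%.
- Case B: DE = 1 + 9 × 0.05 = 1.45; effective n = 100/1.45 = 68.97; noncentrality 2.936; power 83.6%.

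Both round to the stated 84%, so the formula is identified and the clustering itself was allowed for.

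**Step 2: power of a test that holds 5%.** Keep the same noncentrality, but use the noncentral t with 20 − 2 = 18 df, or 17 df once hospital enters as a provider-level covariate.

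| | Normal | t, 18 df | t, 17 df | Difference detectable with 84% power (18 df) |
|---|---|---|---|---|
| Case A | 84.2% | 80.0% | 79.7% | 0.528 SD |
| Case B | 83.6% | 79.3% | 79.0% | 0.532 SD |

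Simulating a t-test on provider means (200,000 runs) gave 80.1% and 79.3% power, with type I error of 5.0% in both cases.

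**Step 3: error rate of an uncorrected GEE test.** With 10 equal clusters per arm and no covariates, the standard sandwich variance is 9/10 of the unbiased between-provider variance. Rejecting when |z| > 1.96 is therefore the same as rejecting when |t| > 1.96 × √0.9 = 1.859 on 18 df:

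alpha = 2 × P(t18 > 1.859) = 7.9%.

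Simulation on provider means (200,000 runs per setting) agrees:

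| Setting | Sandwich with z |
|---|---|
| Unadjusted, m = 8 and m = 10 | 7.9% |
| Unadjusted, m = 30 | 8.0% |
| With hospital, m = 8 / 10 / 30 / 100 | 8.7% / 8.9% / 8.9% / 8.9% |

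The hospital rows assume that the 20 providers split 12/8; splits of 10/10 and 13/7 gave 8.9% and 9.0%. The Kauermann-Carroll correction with a t reference gave 4.9% to 5.0%.

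The uncorrected test has 86.0% and 85.4% power in the two cases, at about 7.9% alpha. So the stated 84% is the power neither of that test nor of one that holds 5%.

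**Step 4: interval width.** Corrected against uncorrected, unadjusted: 2.101 / (1.96 × √0.9) = 1.13. With hospital: 2.110 / (1.96 × √0.85) = 1.17.

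**Step 5: larger clusters.** The chart-review cluster sizes are not given, so these are assumed values. Power on 18 df for 0.5 SD is:

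- 12 patients, ICC 0.05: 83.7%
- 20 patients, ICC 0.05: 92.3%
- 20 patients, ICC 0.10: 79.3%
- 30 patients, ICC 0.10: 83.4%

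**The case against.** The best reply is that nothing in Section 9 is miscalculated. The 84% figures follow from a standard design-effect formula, and the shortfall is about 4 points. That is true. The issue is the choice of approximation and an omitted method, not a slip.

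Second, the inflated error rate is conditional: it arises only if an analyst picks the uncorrected sandwich with a z reference. That also stands, and the 8 to 9% is a risk the plan leaves open rather than a property it commits to.

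Third, the adjusted model may regain precision. If covariates such as rheumatic disease explained 10% of the outcome variance, with ICC unchanged, power would be 83.9% and 83.3% on 18 df. But that 10% is assumed, and the plan's power statement claims no such gain. The 80% and 79% should therefore be read as figures without any gain from covariates.

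Fourth, the primary outcome is measured in a wider chart-review set than 8 to 10 patients per provider. Power there may be higher, as Step 5 shows, but it depends on an unknown ICC. The error rate does not improve, because it is set by the number of providers. Unequal chart-review clusters make it slightly worse: with an assumed mean size of 30, a coefficient of variation of 0.8 and hospital in the model, simulation (40,000 runs) gave about 9.6 to 9.7% uncorrected and about 5.4% with Kauermann-Carroll and t.

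Finally, this is a pilot. That tempers the severity but does not remove the point, since Aim 1 is stated as an efficacy test with its own alpha and power.

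**Conclusion.** The concern holds. At the stated cluster sizes, a two-sided 5% test with 20 providers has 80.0% and 79.3% power (79.7% and 79.0% on 17 df), about 4 points below the stated 84%. The power loss is modest. The more important gap is that the GEE inference is unspecified: depending on an open choice, the real error rate is about 5% or about 8 to 9%, and intervals differ in width by 13% (unadjusted) to 17% (with hospital). These figures assume equal cluster sizes, normally distributed scores, no loss and no precision gain from covariates. This should be fixed before the data are seen, but it is not a fatal flaw.

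**What to change.** In Section 9:

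1. State that every GEE test and confidence interval for the arm effect, in Aims 1 and 2, uses a bias-corrected sandwich variance (for example Kauermann-Carroll). The reference is t with df equal to the number of providers minus the number of provider-level parameters: 18 unadjusted, 17 with hospital.
2. Restate power as about 80% (8 patients, ICC 0.02) and 79% (10 patients, ICC 0.05), without covariate gain. Alternatively, keep 84% and give the detectable difference as about 0.53 SD.
3. Say that these figures apply to 8 to 10 patients per provider, and that power in the chart-review set depends on its actual cluster sizes and ICC.

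The cost is two or three sentences and no added patients, data or procedures. Intervals will be 13 to 17% wider than uncorrected ones, and the power figure about 4 points lower.

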Once providers agree to participate, they will be randomized to either the intervention or the control arm. They will be stratified by site (MGH vs. BWH/ FH) and gender and then randomized using a random number generator. Providers in both arms will be asked to complete Implicit Association Tests and after, to watch a brief set of freely available educational lessons. Patients will not be directly randomized; they will be in the group assigned to their provider as this is a cluster randomized controlled pilot trial.

**Statement about informed consent:** We have included significant detail in our informed consent however do not provide in-depth explanations about unconscious bias (beyond stating the term) or the ways in which it may manifest itself in an encounter. In addition, we do not provide exact details about the individuation intervention for providers because we do not want to influence the behavior of those randomized to the control arm, and for patients because we want it to feel like an organic part of their encounter. We believe that the intervention (a strategy to help providers get to know their patients a bit better) is no more than minimal risk and that the absence of this specific level of detail in the consent form does not reduce the integrity of the consent or mislead participants.

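### The primary model for the quality score is not named, covariates may enter on observed imbalance, and neither provider gender nor a variance method for 20 clusters is fixed

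*Combined protocol and SAP*

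**What the plan says.** For Aim 1, section 9 (Statistical Analysis) states that "unadjusted and adjusted linear generalized estimating equation (GEE) models that account for patient clustering by providers will be used", with the quality score as outcome and arm as predictor. Neither version is called primary. The adjusted version is to contain "covariates including hospital, and other factors that are either strongly correlated with the dependent variable (e.g. rheumatic disease) or imbalanced between the arms". Hospital is therefore fixed and rheumatic disease is an example. There is no candidate list, no threshold, and no statement that the choice is made before outcomes are seen. Aim 2 inherits the same covariates: "For Aim 2, unadjusted and adjusted linear GEE models will be constructed with a) communication metrics", and likewise for each survey score.

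On randomisation, section 3 says "Rheumatologists will be stratified by hospital and by gender and randomly assigned". It then describes the strata as the main hospitals "and their rheumatology satellite clinic sites, and by provider gender (male or female". Section 5 says "They will be stratified by site (MGH vs. BWH/ FH) and gender and then randomized using a random number generator", and section 6 (Providers) repeats gender and site.

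On power, section 9 says "With 10 providers in each arm (N=20) and 8 patients per provider (N=160), we would have 84% power" for a 0.5 SD difference, with ICC 0.02 and two-sided alpha 0.05. It gives 84% again for 10 patients per provider at ICC 0.05. It states no variance estimator, reference distribution or small-sample correction.

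The outcomes section scores all eligible patients seen in the 6-month period and treats the recorded patients as a separate subgroup. Section 3 says of the chart review: "In addition to allowing for a larger sample size for analysis". For the provider IATs, the secondary outcome is change from before to after. Section 9 compares D scores between arms and names no model.

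**The concern.** When two models are planned for one hypothesis and neither is primary, the analyst can pick between them after seeing both. If the null is true, that freedom raises the false-positive rate. If there is an effect, the conclusion can depend on the pick. Entry on observed imbalance adds another choice made after randomisation. Section 10 keeps de-identified data open to the pilot lead and co-investigators throughout, where applicable, so a dated prespecification would be the natural safeguard.

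Two smaller matters sit beside this. The analysis should reflect the randomisation, and gender is a stratum that the model does not fix. With 20 clusters, the type I error of a GEE test depends heavily on the variance estimator and reference distribution, which are not stated.

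**Working it through.** **1. The plan's power figure.** Inputs from section 9: 10 providers per arm, m patients each, difference 0.5 SD, two-sided 0.05. SE = sqrt(2 × (ICC + (1 − ICC)/m) / 10).

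- m = 8, ICC 0.02: SE = sqrt(2 × 0.1425/10) = 0.1688; 0.5/0.1688 = 2.962; normal power = Φ(2.962 − 1.960) = 84.2%.
- m = 10, ICC 0.05: SE = sqrt(2 × 0.145/10) = 0.1703; 0.5/0.1703 = 2.936; normal power = 83.6%.

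Both reproduce the stated 84%. With a noncentral t on 18 df (20 providers less 2), power is 80.0% and 79.3%.

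**2. Unadjusted against hospital + disease, 8 per provider.** Simulation of an exchangeable linear GEE. From the plan: 20 providers, ICC 0.02, 0.5 SD. Assumed: hospital-by-gender strata of 6/6/4/4, three equally common and exclusive diseases, ICC applied to the variance left after disease, no gender effect, and disease explaining 10, 25 or 40% of variance. The calibrated test is a Kauermann-Carroll (KC) sandwich with t on 18, 17 or 16 df. There were 8,000 replicates; the either-model row comes from separate runs of 2,500 and 5,000.

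| Disease share | 10% | 25% | 40% |
|---|---|---|---|
| Power, unadjusted | 80.8% | 81.2% | 82.2% |
| Power, hospital + disease | 83.9% | 89.3% | 95.0% |
| Power, with gender added | 83.5% | 89.2% | 94.9% |
| Unadjusted and hospital + disease disagree at 0.5 SD | 7.4% | 11.9% | 14.6% |
| Only the unadjusted model significant | 2.2% | 1.9% | 0.8% |
| Type I error, each model alone, KC with t | 5.2-5.3% | 5.1-5.5% | 5.0-5.3% |
| Type I error, either model may be reported, KC with t | 6.2-6.5% | 7.2-7.3% | 7.5-7.8% |
| Type I error, uncorrected z: unadjusted | 8.2% | 8.1% | 8.2% |
| Same: hospital + disease | 9.4% | 9.9% | 9.9% |
| Same: gender added | 10.5% | 10.8% | 10.9% |

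The 2,500-replicate run gave 7.4-8.0%, 8.3-8.9% and 8.8-10.0% for the last three rows, hence about 7-11% overall.

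**3. Chart-review cluster sizes.** By the formula in step 1 at ICC 0.02, 20 per provider gives SE = sqrt(2 × 0.069/10) = 0.1175 and normal power Φ(4.256 − 1.960) = 98.9%. With 40 per provider, SE = sqrt(2 × 0.0445/10) = 0.0943 and power is above 99.9%. Models have little room to disagree there. At a 25% disease share, the unadjusted model and the model with hospital, gender and disease disagree in 1.2% (20 per provider) and 0.05% (40). At smaller assumed effects disagreement returns: 11.1% at 0.35 SD with 20, and 8.8% at 0.28 SD with 40. If disease mix differs strongly between providers (assumed Dirichlet(1,1,1)), disagreement at 0.5 SD is 24.9%, 13.8% and 8.7% with 8, 20 and 40.

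**4. The imbalance rule.** A provider-mean regression with a t reference, 20,000 replicates. Assumed: four patient covariates with coefficient 0.3 SD each, and entry at a 0.2 SD imbalance. With no stratum effects, the imbalance-selected model alone rejects in 4.0% under the null. The better of it and the unadjusted model rejects in 6.2%, and the best of four plausible models in 8.5%. With hospital and gender effects of 0.3 or 0.5 SD, the best-of-four rate is 6.8% or 4.4%, because omitting prognostic strata is conservative and offsets the gain from choosing.

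**5. Gender.** In the same regression, the hospital-only model has type I error of 4.8%, 3.9% and 2.2% as both stratum effects go 0, 0.3, 0.5 SD. With gender added it is 4.9%, 5.1% and 4.9%. In the GEE simulation with gender explaining an assumed 40% of between-provider variance (disease 25%), adding it moves power from 90.1% to 91.0% (ICC 0.02, 8 per provider) and from 89.6% to 92.5% (ICC 0.05, 10 per provider). With no gender effect, adding it changes significance in 0.7-1.6% of trials.

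**6. Unequal clusters.** At an assumed mean of 20 per provider, coefficient of variation 0.7, ICC 0.02 and 25% disease share, KC with t on 16-18 df gave type I error of 6.4-6.8% in one run and 7.6-8.4% in another (Monte Carlo SE about 0.5 point in the latter).

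**7. IAT.** With equal variances and pre-post correlation r, baseline adjustment has variance (1 − r²) / (2(1 − r)) = (1 + r)/2 of that for change scores: 0.65, 0.75, 0.85 at assumed r of 0.3, 0.5, 0.7. Multiplying by 1 + 1/16 for 10 against 10 providers gives 0.69, 0.80, 0.90.

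**The case against.** The strongest reply is that the 7-15% disagreement uses the recorded-subgroup cluster size, while the outcomes section scores every eligible patient. At the plan's own 0.5 SD, disagreement then almost vanishes. This stands as a limit on that figure. It does not remove the type I concern, because the fall comes from power near 100% at 0.5 SD and says nothing about the null. Section 9 itself powers Aim 1 on 8-10 per provider.

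Second, disagreement is not error. This also stands: most of it is the adjusted model detecting a true effect. The harm is the 6-8% false-positive rate, which is real but modest.

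Third, section 9 does not rule gender out, since its covariate list is open-ended, and does not say that an uncorrected z test will be used. Both are correct. A reader might infer from the reproduced 84% that a z test is planned, but that shows only how power was approximated.

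Fourth, a KC correction with t does not hold 5% with unequal clusters. Providers qualify with one or more sessions a week and contribute all eligible patients, so unequal clusters are likely. This stands and shapes the fix.

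Fifth, a change-score comparison of the IATs is valid. Agreed; baseline adjustment is a matter of efficiency.

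**Conclusion.** The point holds as a prespecification gap that should be closed. Section 9 leaves the primary model unnamed, allows entry on observed imbalance, and does not fix a randomisation stratum. No other section supplies these.

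At 8 per provider, freedom between two plausible models puts type I error at about 6-8% with a calibrated test. With an uncorrected sandwich z test, each model alone would be at about 7-11% with equal clusters, and higher with unequal ones. The stated power holds only with a normal reference; on t with 18 df it is about 80% and 79%.

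Three stronger readings are not supported. Leaving out gender does not bias the estimate or inflate type I error with a calibrated test; it is mildly conservative and a minor component. The plan does not commit to an invalid test; it is silent. And 7-15% of trials reaching a wrong conclusion does not follow: only the unadjusted model is significant in 0.8-2.2%.

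Variance shares, stratum sizes, disease mix and cluster-size spread are all assumed. The disagreement figure is sensitive to them, from 0.05% to 24.9% at 0.5 SD across the cases shown. The textual gap and the power recalculation do not depend on them.

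**What to change.** In section 9:

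- Name one primary model in advance: quality score on arm, hospital stratum as actually randomised, provider gender and rheumatic disease, with a coding rule for patients who have more than one disease. Label the unadjusted and any other adjusted models supportive.
- Remove observed imbalance as a reason for entering a covariate.
- State a small-sample-corrected GEE variance with a t reference on provider-level df, chosen to hold 5% under the unequal cluster sizes expected in chart review. KC with t on 16-18 df gave about 6-8% there, so check a more conservative correction or Satterthwaite-type df before fixing it.
- Restate power as about 80% and 79% for the t reference.
- Carry the same strata and correction into the Aim 2 models.
- Reconcile sections 3 and 5 on whether satellite sites are strata.

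As a separate minor improvement, compare follow-up IAT D scores between arms with baseline D score as covariate.

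The cost is wording; the variables are already collected. Gender takes one provider-level df (17 to 16), or about 0.1-0.4 power point if it explains nothing; satellite strata would take more. The correction widens intervals. With equal clusters of 8, KC with t lowers nominal power of the proposed model at 0.5 SD from 90.9/94.4/97.8% (uncorrected z, type I error 10.5-10.9%) to 83.5/89.2/94.9% (about 5%) at disease shares of 10/25/40%.
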